Corneal Biomechanics and Corneal Reshaping Therapy NCT02719535 March 25 2016

(a) Introduction

Myopia is highly prevalent in Asian populations, especially Chinese populations [1], and now affects Americans and Europeans as well.[2-3] Low to moderate myopia is not a major concern, but high myopia (more than 6D) is associated with retinopathy and glaucoma and is an economic burden on society.[4]

Various treatment options have been proposed to reduce the progression of myopia, including the use of pharmaceutical agents and different types of corrective lenses. [5-8] Corneal reshaping, also called orthokeratology, is an intervention with proven efficacy in retarding myopia progression. [10]

In orthokeratology, the corneal curvature is altered after a patient wears the lenses. The effective treatment range is usually not more than 5D of myopia and not more than 1.5D of astigmatism. In addition, orthokeratology can be slow or ineffective in some patients. This may be related to the pre-treatment corneal parameters such as the apical radius and eccentricity.[11] Corneal biomechanical properties may also be a factor, but accurate measurement of the influence is difficult.

Most interventions for myopia control begin in early childhood. After commencement of the treatment, several years of continual monitoring is required to confirm its efficacy. If the intervention is eventually ineffective, then the time would have been wasted. The goal of the proposed study is to investigate whether corneal biomechanics are predictive of successful orthokeratology. If pre-treatment corneal biomechanics combined with other conventional corneal parameters do not indicate successful orthokeratology, patients can be advised to try other more effective interventions earlier.

(b) Objectives

- 1. To monitor the changes of corneal biomechanics from long-term (6 months) successful orthokeratology
- 2. To determine if corneal biomechanics is predictive of the rate of orthokeratology

(c) Methods

Subjects

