Young, healthy, myopic adults with no history of long-term contact lens wear and ocular disease were recruited. Subjects who occasionally wear soft lenses (such as for sports) were eligible. The inclusion criteria included myopia between -4.00D and -5.00D sphere, and with-the-rule astigmatism (axis 180 ± 30) of not more than 1.50D, where the spherical equivalent was between -4.00D to -5.75D. The difference in myopia between the two eyes was within 1D for both the sphere and cylinder components. The inclusion criterion in refractive error for this study is to eliminate the confounding factor for orthokeratology caused by a wide refractive range. The best-corrected visual acuity was at least 0.10 logMAR in each eye when measured using the Early Treatment Diabetic Retinopathy Study (ETDRS) charts (Prevision Vision, La Salle, IL) under a normal room lighting condition.

Procedures

The following baseline data were collected: non-cycloplegic manifest refraction, ocular biometry through partial coherence interferometry (Zeiss IOLMaster; Zeiss Humphrey, Dublin, CA), corneal topography (Medmont E300, Medmont Pty Ltd., Vermont, VIC, Australia), corneal thickness through swept-source optical coherence tomography (Casia SS-1000, Tomey, Nagoya, Japan), and corneal biomechanics using an Ocular Response Analyzer (ORA; Reichert Inc., USA).

Five valid axial length measurements were captured using the IOLMaster, and an average reading was generated for analysis. In corneal topography, three images (scores higher than 95) were automatically captured. The mean value of the simulated steepest and flattest keratometry readings was used for analysis. Corneal thickness was measured using a "3D Corneal Map" scan by the swept-source optical coherence tomography. Three automated measurements were obtained for each scan while the subject focused on a central target inside the instrument. In ORA, three acquisitions were obtained each with a waveform score of at least 6.0. Corneal hysteresis (CH), corneal resistance factor (CRF), and corneal-compensated intraocular pressure (IOPcc) were measured.

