Ethics clearance was obtained from the institutional review board of The Hong Kong Polytechnic University. Informed consent was obtained from all participants included in the study. This study was registered at ClinicalTrials.gov (NCT02719535, registered March 25, 2016) and in the University of Hong Kong HKU Clinical Trials Register (HKUCTR-1957, registered Feb 1, 2016).

Analysis of data

The corneal parameters and refractive error obtained in each aftercare visit were compared with the baseline data. Data of one eye of each subject who completed the 6-month orthokeratology were analyzed, with the eye with residual sphere closer to plano at the 6-month visit being selected. If the residual sphere was the same in both eyes, then the eye with less residual astigmatism was selected. For subjects with the same residual refractive errors in both eyes, the right eye was selected. Normality was checked using the Shapiro-Wilks test. Repeated-measure analysis of variance or the Friedman test were used to compare changes in ocular parameters throughout the study, that is, from baseline to the end of the 6-month orthokeratology. Baseline ocular parameters that could best predict myopia reduction were identified through linear regression (Pearson or Spearman). Reduction of sphere at the 6-month visit was used as the dependent outcome response, and the various baseline ocular parameters were treated as independent predictors. All data analysis and graphical presentation were completed using SigmaPlot 13 (Systat Software, Inc.).

(d) References

- 3. Pärssinen O. The increased prevalence of myopia in Finland. Acta Ophthalmol. 2012;90: 497-502.

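### Myopia reduction is modelled as sphere alone, so corrected astigmatism earns no credit and induced astigmatism no penalty; the regressions should also be run on spherical equivalent

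*Combined protocol and SAP*

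**What the plan says.** The second objective in section (b) is "To determine if corneal biomechanics is predictive of the rate of orthokeratology". The analysis that serves it is in section (c), Analysis of data: "Baseline ocular parameters that could best predict myopia reduction were identified through linear regression (Pearson or Spearman"). Its response is then fixed: "Reduction of sphere at the 6-month visit was used as the dependent outcome response". Neither cylinder nor SE is named as a response.

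Elsewhere the plan does take account of astigmatism:

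- **Entry limits (Subjects).** Sphere: "The inclusion criteria included myopia between -4.00D and -5.00D sphere". Cylinder: "with-the-rule astigmatism (axis 180 ± 30) of not more than 1.50D". SE: "the spherical equivalent was between -4.00D to -5.75D".
- **Choice of the analysed eye (Analysis of data).** The eye whose remaining sphere is nearer zero is taken. If the two eyes tie, "then the eye with less residual astigmatism was selected".
- **Data collected.** Manifest refraction is taken at baseline (Procedures) and subjective refraction at every follow-up visit (Wearing schedule), so cylinder is available throughout.
- **Longitudinal comparison (Analysis of data).** Refractive error at each aftercare visit is compared with baseline. The components are not specified, and this is not the prediction analysis.

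**The concern.** In minus-cylinder form, sphere is the power of the less myopic meridian. An outcome built on sphere follows that meridian only and does not register what happens in the other one. Two eyes with the same sphere reduction can finish with different overall myopia, and the regression treats them as equal responders.

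A baseline corneal parameter related to change in astigmatism could therefore look stronger or weaker as a predictor of myopia reduction than it would on a scale that includes both meridians. The eye-selection rule leans the same way, because astigmatism counts there only when spheres tie. The Introduction says the results may be used to steer patients toward other interventions sooner, so a predictor should not depend on which refractive scale was used.

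**Working it through.** **Inputs, all from section (c), Subjects and Analysis of data.** Baseline sphere -4.00 to -5.00 D; astigmatism at most 1.50 D; SE -4.00 to -5.75 D; response = reduction of sphere at 6 months.

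**Step 1: reproduce the plan's SE range.** SE = S + C/2.

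- Minus-cylinder form: -4.00 + 0 = -4.00 D and -5.00 - 1.50/2 = -5.75 D. This matches the stated range exactly.
- Plus-cylinder form: -4.00 + 1.50/2 = -3.25 D and -5.00 + 0 = -5.00 D. This does not match.

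The plan's sphere is therefore the minus-cylinder sphere.

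**Step 2: relate the two outcomes.** With C negative or zero, SE = S - |C|/2. Subtracting baseline (0) from month 6 (6):

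sphere reduction = SE reduction + (|C6| - |C0|)/2.

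This is an identity. At equal SE reduction, induced cylinder raises the sphere score and corrected cylinder lowers it. At equal sphere reduction, corrected cylinder goes unrecorded and induced cylinder costs nothing.

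**Step 3: put numbers in.** Each eye starts at -4.50 D sphere and ends at plano sphere.

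| Eye | Baseline | Month 6 | Sphere reduction | SE reduction |
|---|---|---|---|---|
| A, cylinder fully corrected | -4.50/-1.50 | 0/0 | 4.50 | 0 - (-5.25) = 5.25 |
| B, cylinder unchanged | -4.50/-1.50 | 0/-1.50 | 4.50 | -0.75 - (-5.25) = 4.50 |
| C, 1.50 D induced (assumed) | -4.50/0 | 0/-1.50 | 4.50 | -0.75 - (-4.50) = 3.75 |

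- A versus B uses only the documented entry limit: 5.25 - 4.50 = 0.75 D.
- A versus C needs an assumed amount of induced cylinder. The SE gap is (1.50 + induced)/2, which gives 1.00, 1.25 and 1.50 D for 0.50, 1.00 and 1.50 D induced.

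**Step 4: eye selection.** By the stated rule, an eye at 0/-1.50 (SE -0.75 D) is chosen over its fellow at -0.25/0 (SE -0.25 D).

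**Step 5: how far the two outcomes could diverge across subjects.** The documents give no standard deviations, so this is illustration only. Assume that cylinder reduction is independent of sphere reduction, with SD 0.25 to 0.50 D for cylinder and 0.25 to 0.75 D for sphere. Then

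correlation = SDsphere / sqrt(SDsphere² + SDcyl²/4).

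- Lowest: 0.25 / sqrt(0.0625 + 0.0625) = 0.71.
- Highest: 0.75 / sqrt(0.5625 + 0.0156) = 0.99.

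The scales could be nearly interchangeable or materially different.

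**The case against.** The strongest reply is that sphere is a legitimate choice. The plan states its myopia criterion in sphere and picks the eye mainly on sphere, and nothing in it makes SE the target. To say that sphere credits induced astigmatism assumes that SE is the true effect. SE also hides things: -4.50/0 going to 0/0 and -4.50/0 going to +0.75/-1.50 both give 4.50 D of SE reduction, yet the residual cylinders differ by 1.50 D. Any single number loses information about astigmatism. This stands, and it is why sphere should be kept and not replaced. It does not remove the case for a second scale, because the plan's usage is mixed: it sets an SE limit at entry and counts cylinder in both the between-eye criterion and the eye tie-break.

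Three stronger readings are tempting and are not supported:

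- **That eyes with equal scores differ by up to 1.50 D in treatment effect.** For full versus no correction, 1.50 D is the difference in cylinder, or in the more myopic meridian (6.00 versus 4.50 D). On SE it is 0.75 D. Reaching 1.50 D on SE needs another eye to gain an assumed 1.50 D. The plan's 1.50 D limit applies to astigmatism at entry, not to induced astigmatism, so 1.50 D is not a bound either.
- **That cylinder change accounts for a known share of the outcome variance.** Assuming independent cylinder change with SD 0.25 to 0.75 D and SE-reduction SD 0.3 to 0.5 D, the share runs from 0.0156/0.2656 = 6% to 0.1406/0.2306 = 61%. None of these SDs is in the documents. Nor does the 1.00 D entry window show that responses vary little: it restricts baseline sphere, and the Introduction notes that response differs between patients.
- **That a predictor would come out with the wrong sign.** That would need an association with cylinder change large enough to outweigh an opposite one with SE reduction. None is shown.

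**Conclusion.** The point holds as a minor limitation of outcome definition. The sole response in the prediction analysis ignores corrected cylinder and does not penalise induced cylinder. This follows from the minus-cylinder form, which the plan's own SE range confirms. Within the documented limits, full versus no correction of eligible cylinder leaves up to 0.75 D of SE difference unseen at equal sphere reduction. The difference is larger if treatment induces cylinder, by an amount the documents do not bound. Whether any predictor would change cannot be judged from the documents, because the spread of cylinder change is not given. The plan does not contradict itself, and sphere reduction is not an invalid outcome.

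**What to change.** - Keep reduction of sphere at 6 months as a response and fit the same regressions to reduction of SE at 6 months, on the same eyes.
- Adjust each regression for the baseline value of the measure modelled. This matters more for SE, whose entry range is 5.75 - 4.00 = 1.75 D against 1.00 D for sphere. The adjustment needs a second term in the model; a simple correlation cannot provide it.
- Report cylinder change from baseline to 6 months, so that readers can see how far the two scales could differ.
- Name a baseline parameter as a predictor of myopia reduction only if the conclusion holds on both scales. If it holds on one, say which.

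**Cost.** One derived variable from refraction already recorded, and a second set of regressions. No new measurements or visits are needed. SE carries the measurement error of the cylinder as well as of the sphere, and requiring agreement on both scales is slightly more conservative.
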